This application is based on the premise that probationers and parolees must have access to stable, drug free housing to reduce HIV risk, access needed services and avoid rearrests and reincarceration. Drug free housing at the Sober Living Network (SLN) in California will be studied as a way to provide a positive living environment for probationers and parolees. The houses use a sober living house (SLH) model of recovery that includes a communal recovery environment, abstinence from drugs and alcohol, peer support, and encouragement to attend self-help groups such as Alcoholics Anonymous. Preliminary data based on a sample of 300 individuals entering 20 SLHs in California showed resident improvement in a variety of areas, including drug and alcohol use, employment, psychiatric symptoms, and arrests ([name] et al., 2010). Although residents referred from parole and probation systems had substance use reductions that were comparable to voluntary residents, they had had far more problems maintaining employment, higher rates of arrest and incarceration, and lower attendance at self-help groups ([name], et al., 2010). Thirty seven percent had been rearrested at 6 month follow-up and one reason may be that probationers and parolees received only 35% of the services that they felt they needed to succeed. Although over half met DSM IV criteria for methamphetamine dependence during the last year, a very high risk group for HIV, we did not assess HIV outcomes.

The proposed study will improve SLHs for offenders by adding a Motivational Interviewing Case Management (MICM) intervention specifically targeted to the problems presented by each offender. The list of potential problems that MICM can address is extensive: 1) adapting to the SLH environment, 2) complying with parole and probation, 3) finding and maintain work, 4) successfully accessing and maintaining retention in services, 5) addressing HIV risk, testing and treatment, 6) mobilizing personal and informal resources, and 7) managing setbacks (e.g., relapse, loss of housing, loss of work).

Men and women offenders (N=330) entering SLHs will be assigned to a condition consisting of drug free housing and provision of a resources manual where residents can seek help for a variety of problems (a control group) or drug free housing plus the MICM (intervention).

**Aim 1:** To assess HIV testing rates, HIV risk behaviors, and utilization for HIV services at baseline, 6, and 12 months.

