For estimation of power in growth curve modeling, programs for estimating power are available (Bosker, 1999), but they typically require population parameters, including between- and within-subjects covariance matrices and estimates of level 1 and 2 residual variances. Other methods have been developed for testing specific slope differences (Jung & Ahn, 2005), but point estimates are still required for the variances of the slope parameter within each group for which prior information, and even ranges of plausible values, are simply not available. Instead of assuming knowledge of such population parameters, power is approximated here in the

Min N for Power=.8 in Longitudinal Models with Continuous Outcomes					
		Δ (%)			
		.2	.3	.4	.5
δ	.2	146	65	37	24
	.5	208	93	52	34
	.8	270	120	68	44

context of longitudinal Generalized Estimating Equations (GEE) models (Diggle, et al., 2002) using the attrition adjusted effective sample sizes. Various possible error variance structures in GEE models can approximate the partitioning of variance explicit in multilevel models and also provide a simpler context in which to approximate power for between groups longitudinal effects as it instead

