relies only on an effect size defined in standardized units as $\Delta = d/\sigma$, where d effect size (here, the time averaged difference in the outcome variable between the two comparison groups) and σ is the unknown level 1 error variance. Assuming $\alpha=.05$ and $n=3$ interviews per respondent, the minimum sample sizes required to detect standardized effect size differences of $\Delta=(.2, .3, .4, .5)$ for exchangeable error correlation values of $\delta=(.2, .5, \text{ and } .8)$ with power of .80 are shown in the table above. Power for estimation of individual level effects associated with the first two levels comprising interviews nested within individuals uses a design effect adjusted sample size accounting for within-house correlation of responses. Assuming a medium Intraclass Correlation Coefficient of .06 (Kirk, 1995) reduces the effective attrition adjusted number of respondents from 132 to $n=132/(1+32*.06)=45$ cases. From the table, power would be close to .80 to detect small-to-medium effect size differences ($\Delta=.35$, as defined in (Cohen, 1988) in the time averaged differences between the two treatment groups when the error correlation over time is relatively moderate ($\delta = .2$). Power for estimation of level 3 coefficients is approximated in the context of simple linear regression with $n=32$ cases (houses) available. Power to detect medium to large effect size relationships ($f^2=.25$) (Cohen, 1988) between house level characteristics and time averaged differences in outcomes between the two treatment conditions would be .81.

The meta-analysis on MI outcome by Hettema et al. (2005) found pairwise between group effect sizes to be .77 (very large) in the short term and .30 at (small-to-medium) one year follow up. Therefore, power should be more than adequate.

Management Plan

The management plan is based on procedures from our recent study of SLHs (i.e., [name] et al., 2010) as well as previous multisite studies where [name] served as key personnel (Carroll et al., 2006). Coordination will be achieved using weekly telephone conference calls involving all staff on the research team. [name] and [name] will travel to Los Angeles at least quarterly for day long face to face meetings with fieldwork staff and therapists. Study therapists will be hired by [name] who will train them together (16 hours face to face) and meet with them via telephone conferencing weekly to discuss all aspects of MICM.

Timeline

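### The power section reports that no prior variance information exists and reads power at one favourable correlation, although the team's own 300-resident study could supply at least plausible ranges for the non-HIV outcomes

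*SAP*

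**What the plan says.** In Power Considerations, the SAP explains why it does not compute power for the growth model. Methods for slope differences exist, it says, but they need each arm's slope variance, "for which prior information, and even ranges of plausible values, are simply not available". It turns to a GEE approximation for a time-averaged difference and tabulates the minimum N for three over-time error correlations: delta .2, .5 and .8.

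Two generic inputs follow. The house effect is set by "Assuming a medium Intraclass Correlation Coefficient of .06", cited to a textbook, which reduces 132 per group to 45. Power for an effect of .35 is then put near .80 "when the error correlation over time is relatively moderate", meaning delta .2. The section ends by calling power more than adequate, citing a meta-analytic motivational interviewing effect of .30 at one year.

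Protocol section A says: "Preliminary data based on a sample of 300 individuals entering 20 SLHs in California showed resident improvement in a variety of areas". The areas it names are arrests, substance use, work and psychiatric health. It reports that "Thirty seven percent had been rearrested at 6 month follow-up" among residents referred from probation and parole, and adds that "we did not assess HIV outcomes". The SAP's Management Plan refers to a recent sober living house study by the same team, also cited to 2010, and builds on its procedures. The power section takes no figure from that work.

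**The concern.** A repeated-measures study of residents nested in 20 houses carries information on the three quantities that the power section lacks: how alike residents of one house are, how strongly a resident's outcome correlates over time, and how much change varies between residents. The outcomes named for it overlap with H2.1 to H3.3. Saying that not even plausible ranges exist does not fit with having such a study, at least for those outcomes in residents without MICM.

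The substitutes also matter. The table has three rows for delta, but the conclusion is read from the lowest. For a time-averaged difference that row is the most favourable, so describing it as moderate misleads. At stake is whether the stated power gives a sound basis for saying that 330 participants are enough.

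**Working it through.** **Inputs (SAP, Power Considerations).** 132 per group after attrition; ICC .06; multiplier 32; 3 interviews; effect .35; alpha .05; delta .2, .5, .8. Two-sidedness is stated only for the simple two-group test, not for the table.

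**1. Reproduce the table.** For a time-averaged difference with exchangeable correlation,

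n per group = 2(z_alpha + z_power)^2 (1 + 2·delta) / (3·effect^2).

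At effect .2 and power .80:

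| delta | SAP | one-sided .05 (z = 1.645) | two-sided .05 (z = 1.960) |
|---|---|---|---|
| .2 | 146 | 144.3 | 183.1 |
| .5 | 208 | 206.1 | 261.6 |
| .8 | 270 | 267.9 | 340.1 |

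The other nine cells behave the same way. The table therefore rests on a one-sided alpha that the SAP does not disclose.

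**2. Reproduce the effective sample size.** 132/(1 + 32 × .06) = 132/2.92 = 45.2, the SAP's 45.

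**3. Power on the SAP's own inputs.** Power = Phi(effect × sqrt(3n/(2(1 + 2·delta))) − z), with n = 45 and effect .35. At delta .2 one-sided: .35 × sqrt(135/2.8) = 2.430; 2.430 − 1.645 = .785; power .784. This is the SAP's value near .80.

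| delta | one-sided | two-sided |
|---|---|---|
| .2 | .784 | .681 |
| .5 | .651 | .529 |
| .8 | .555 | .430 |

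The ICC is held at .06 throughout, so the whole fall comes from delta. One-sided, 80% power needs 47.1, 67.3 and 87.5 per group at delta .2, .5 and .8, against 45. At the cited one-year effect of .30, power is .669, .539 and .454 one-sided, or .549, .414 and .333 two-sided.

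**4. How far this depends on the multiplier.** The SAP multiplies the ICC by 32, its number of houses. The usual design effect uses residents per house minus one: 264/32 = 8.25, so 132/(1 + 7.25 × .06) = 92.0. With the 70 houses of the protocol, 264/70 = 3.77 and effective n is 113.2. Power for the time-averaged test at effect .35, ICC .06:

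| delta | n = 92, one-sided | n = 92, two-sided | n = 113, two-sided |
|---|---|---|---|
| .2 | .966 | .935 | .971 |
| .5 | .897 | .828 | .897 |
| .8 | .817 | .722 | .807 |

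The ICC matters too. Over an assumed range of .01 to .10, effective n runs from 123 to 77 with 32 houses and from 128 to 103 with 70.

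**5. The test actually planned.** Under Analysis of Specific Aims, evidence for H1.1 is a treatment coefficient on the rate of change, and Aim 3 uses the same method. With three equally spaced interviews and exchangeable errors, the fitted slope is half the first-to-last difference, whose variance is 2(1 − delta) in outcome-SD units. For a difference in change of .35 SD, power = Phi(.35 × sqrt(n/(4(1 − delta))) − z). At n = 45 one-sided this gives .37, .51 and .84 at delta .2, .5 and .8 (two-sided .26, .38 and .75). At n = 92 two-sided it gives .47, .66 and .96. Delta .2 is now the least favourable value. These figures are illustrative: they carry over the same effective n, although the house ICC for change may differ.

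**6. What the earlier study could give.** The number of waves, house sizes and follow-up rate are not stated. Assuming 20 equal houses of 15, the large-sample SE of an ICC near .06 is sqrt(2 × (.94 × 1.84)^2/(15 × 14 × 19)) = .039. Assuming all 300 were seen at two waves, the SE of delta is (1 − delta^2)/sqrt(300), which is .055 at delta .2 and .043 at .5. Delta would be known fairly well and the ICC only roughly.

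**The case against.** The SAP's sentence is narrower than it first appears. It concerns slope variances within each group and never says that the ICC or delta is unavailable. The earlier study, as described, had no MICM arm, mixed offenders with voluntary residents, and did not measure HIV outcomes, whereas this trial enrols only offenders who are HIV-positive or at high risk. All of this stands. The conflict with the protocol is therefore partial: a relevant source exists and is unused, but it would not supply every missing input. Its ICC, with an SE of about .04, would be imprecise. The documents do not show whether the data are still held or in usable form.

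The table also prints required N for all three values of delta, so the sensitivity is disclosed. That stands as well, but the conclusion is drawn from one row only.

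A reader might infer that the trial's power is really as low as .56. The documents do not support that. The figure inherits the multiplier of 32; with residents per house in its place, one-sided power for the same test stays above .80 at every tabulated delta. A reader might also infer that delta .2 flatters the whole plan. It flatters the time-averaged approximation only; for the slope test it is the least favourable value.

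**Conclusion.** The point holds in limited form. Saying that not even plausible ranges exist is too strong, because the team's own study could give them for substance use, employment and arrests in residents without MICM. On the SAP's inputs, its claim of power near .80 holds at best for one of three rows: .78, .65 and .56 one-sided, or .68, .53 and .43 two-sided. The closing statement that power is more than adequate does not follow, since it cites an effect of .30, below the .35 used.

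These numbers assess the SAP's calculation, not the trial. They rest on n = 45, ICC .06 and the time-averaged test. With about 8 analysed residents per house, two-sided power is .94, .83 and .72, and for the rate-of-change test the ordering across delta reverses. The documents do not settle the true power in either direction, which is why the inputs should be estimated or shown as ranges.

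**What to change.** In the SAP's Power Considerations:

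- Qualify the availability sentence: no prior data for the MICM arm or for HIV outcomes, but earlier data on other outcomes in sober living house residents.
- From the earlier study, where the data allow, estimate the house ICC, the over-time correlation and the variance of change for substance use, employment and arrests, each with its uncertainty. Use the residents on probation or parole where numbers permit. If the data cannot be used, say why.
- Stop describing delta .2 as moderate.
- Restate power two-sided for the slope test actually planned, across delta .2 to .8 and a range of ICC, with a design effect based on residents per house. For HIV outcomes, show ranges only.

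The cost is a small reanalysis, if the earlier data are accessible, and a rewritten power section. The design does not change. The stated power may move up or down.

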### **Sample Characteristics**

Three hundred and thirty SLH residents who are on probation or parole and are HIV+ or at high risk for HIV will be recruited into the study within their first month of entering the SLH. The director of the Sober Living Network in Southern California, [name], states over 60 houses in Los Angeles County accept large numbers of male and female offenders and the vast majority will be willing to participate in the study. This is consistent with our previous study of SLHs, where less than 5% of potential participants declined to participate. Belenko (2006) has documented that criminal justice offenders have very high rates of HIV infection and high risk behaviors. This supports the feasibility of meeting our recruitment goal to enroll HIV+ or high risk individuals. To be parsimonious in our efforts, we will select the 70 houses with the largest number of offenders admitted. Half of the houses (N=35) will be gender specific for men and half (N=35) will be gender specific for women. Stratified random sampling procedures will be used to ensure an equal number of male and female houses within each study condition. Thus, individuals enrolled in houses assigned to the MICM condition will receive that intervention and individuals assigned to the comparison condition will receive SLH services as usual along with a list of referral resources for a wide variety of problems. Risks for contamination of intervention effects on non-intervention offenders are eliminated because of our randomization of houses. These procedures will enable us to reach our target recruitment with an average of only 10.3 residents per house over 3 years of recruitment. We will randomize more houses if we need them to meet our recruitment goals.

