## **Research Interviews**

Residents who are interested in participating will attend a research interview that will begin with an assessment of inclusion/exclusion criteria. Those who meet the criteria will be administered the baseline interview after they are consented.

Randomization will occur at the house level, so individuals in houses randomized to the MICM condition will receive that intervention and individuals in houses assigned to the comparison condition will receive SLH services as usual along with a list of referral resources for a variety of problems. Using an “Intent to Treat” design, all participants will be followed up at all of the time points even if they leave the SLH immediately after completion of the baseline interview. Follow-up interview procedures will include updating contact information at each interview as well as at 3 and 9 months. During these interim 3- and 9-month contacts, we will first reach out to participants by phone and, if we were unsuccessful, we would send a letter encouraging them to call us. Those who we were able to speak with would receive a \$5 gift card at the 3-month contact and a \$10 gift card at the 9-month contact. For participants who are difficult to reach we will use tracking methods described by Anglin et al (1996). They include procedures to utilize contact information from respondents’ families and friends and locating participants in jails, prisons, and other institutions. Participants will receive \$30 for the baseline interview and \$50 for interviews at 6- and 12-month follow up. We expect baseline sessions to last 2 hours and follow up sessions to last about 90 minutes. We are using Survey Gizmo as the platform for the interviews, which will require an internet connection for us to access the survey. The connection being used while transferring data between ARG equipment and Survey Gizmo will be protected by a 128-bit encrypted SSL tunnel so as to prevent confidential data from being sniffed. Interviewers will conduct interviews only on ARG laptops, which will be password protected and configured on the ARG secure network.

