Hypotheses H1.1 will be tested in the framework of longitudinal models, as described above. The focus is on treatment condition which, although uniquely assigned to individuals, is implemented at the house level and therefore will be treated as a level 3 variable. This allows for a limited exploratory examination of potential treatment effects with house level characteristics. Interactions of treatment condition with level 2 variables (e.g., gender) can be implemented by simply including treatment as a predictor of the non-randomly varying level 2 coefficient (e.g., gender) of interest. Evidence in favor of the hypotheses will be significant level-3 coefficients (the relevant γ coefficient) for the indicator variables (Z) representing average differences between houses in the rate of change in the outcome over time (i.e., the intercept of the level 2 slope parameter $\lambda_{o,h}$).

Aim 2: *To compare baseline substance use within each study condition with 6- and 12-month substance use.*

H2.1 Residents in each study condition will show significant reductions in drug and alcohol use between baseline and follow-up time points as measured by the Time Line Follow Back (TLFB).

H2.2 Residents in each study condition will show significant reductions in drug and alcohol problems between baseline and follow-up time points as measured by the Addiction Severity Index alcohol and drug scales.

Hypotheses H2.1 and H2.2 will be tested in the framework of longitudinal models, as described above. As a first step, an empty model will be estimated (random intercept and slope but no level 2 (individual) or level 3 (house) covariates) to test whether the variances of the intercept and slope parameters (u and v) are significant. Should significant variation be found, candidate covariates, both at the individual level (level 2) and the house level (level 3), will be considered in separate models and any such covariates will be entered as predictors of both the random intercept and slope.

Aim 3: *To compare outcomes between the two study conditions at baseline, 6, and 12 months.*

H3.1 Residents receiving MMI in addition to drug free housing will have less substance use (TLFB) and lower ASI alcohol and drug severity than the drug free housing and resources condition.

H3.2 Residents receiving MMI in addition to drug free housing will have fewer arrests, fewer days incarcerated and lower ASI legal severity than the drug free housing and resources condition.

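### The SAP's house-level power of .81 is stated for a between-condition difference that no single house can have, and it does not give the power of the treatment comparison at .35 or .30

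*SAP*

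**What the plan says.** The Protocol (Research Interviews) states: "Randomization will occur at the house level, so individuals in houses randomized to the MICM condition will receive that intervention". Sample Characteristics draws the consequence: "Risks for contamination of intervention effects on non-intervention offenders are eliminated because of our randomization of houses". A house is therefore in one condition only.

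Under Analysis of Specific Aims, Aim 1, the SAP says that treatment condition "is implemented at the house level and therefore will be treated as a level 3 variable". Evidence for H1.1 is a significant level 3 coefficient for condition on the rate of change. H3.1 to H3.3 are to be tested by the same methods.

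Under Power Considerations, the SAP says that power for level 3 coefficients "is approximated in the context of simple linear regression with $n=32$ cases (houses) available". At f²=.25, power for the relation "between house level characteristics and time averaged differences in outcomes between the two treatment conditions would be .81". The section then cites a meta-analysis of motivational interviewing, with between-group effects of .77 in the short term and .30 at one year, and concludes that power is ample.

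**The concern.** A simple regression with houses as cases needs one outcome value per house. As worded, that value is the difference between the two conditions, which would require residents of both conditions in the same house. The design rules this out, so the .81 is attached to a quantity the trial will not produce.

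The label matters because this is the only power figure described as level 3, and level 3 is where the SAP tests the treatment hypotheses. A reader may take .81 as power for the treatment comparison. The SAP does not say whether it means a house characteristic, condition, or an interaction of the two, and the effect size behind the figure means something different in each case.

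**Working it through.** **Inputs.** From SAP Power Considerations: 32 houses, f²=.25, stated power .81, 264 analysed (132 per group), ICC .06, effects of .35, .30 and .77. Alpha .05 is given for the neighbouring table ("Assuming $\alpha=.05$ and $n=3$ interviews per respondent") and a two-sided test for the .82 figure; I assume that both carry over. House counts elsewhere: 70 (Protocol, Sample Characteristics and Design Summary) and 30 (Protocol, House Environment). My assumptions: houses split equally between conditions, equal house sizes, and one outcome per person with total variance 1.

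**1. The plan's figure.** For one predictor, the noncentrality is n × f² = 32 × .25 = 8.
- Normal approximation: Φ(√8 − 1.96) = Φ(2.828 − 1.960) = .807, which rounds to .81.
- Exact noncentral F with 1 and 30 df: .781.

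The .81 is therefore an ordinary one-predictor regression with one outcome value per house. That is valid if the value is a house mean or mean change, but not if it is a between-condition difference.

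**2. Read as power for condition.** For a balanced two-group predictor f² = D²/4, with D in SDs of house means. So f²=.25 gives D = 2 × √.25 = 1.0.

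To convert to person-level SD with 32 houses:
- Analysed per house: 264/32 = 8.25.
- Variance of a house mean: .06 + .94/8.25 = .174; SD .417.
- f²=.25 therefore corresponds to d = 1.0 × .417, about .42.

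**3. Power for condition at the SAP's effect sizes.** Standard error of the difference = √(2 × variance of a house mean / houses per arm). The noncentral t has (houses − 2) df.

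| Houses | Per house | Variance of house mean | SE | Power, d=.35 | Power, d=.30 |
|---|---|---|---|---|---|
| 32 | 8.25 | .174 | √(2×.174/16) = .147 | .63 | .50 |
| 70 | 3.77 | .309 | √(2×.309/35) = .133 | .74 | .60 |
| 30 | 8.80 | .167 | √(2×.167/15) = .149 | .62 | .49 |

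With 32 houses and d=.35, power is .76 at ICC .01 and .55 at ICC .10. At the short-term .77 the noncentrality is .77/.147, about 5.2, and power exceeds .99.

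**4. Read as moderation by a house characteristic.** This needs condition, characteristic and product in the model, leaving 32 − 4 = 28 error df. At partial f²=.25 the noncentral F gives .72 with noncentrality .25 × 28 = 7, and .78 with .25 × 32 = 8. On the convention of step 1 it is .78, almost the same as the simple regression.

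**The case against.** The strongest reply is that only the last clause is loose. The preceding sentence says that the figure is for level 3 coefficients in a regression on houses, and the trial plans such analyses. The SAP's HLM section asks whether houses differ on outcomes, the Protocol's House Environment section relates house differences to outcome, and condition is itself a level 3 variable. This stands. A reader might infer that the .81 answers no question the trial can ask; the documents do not support that, because the arithmetic fits a planned house-level main effect.

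Three further inferences also go too far.
- **That the SAP assumed an effect about three times its own .35.** The 1.0 is in SDs of house means and the .35 in person-level SDs. On a common scale the comparison is about .42 with .35 and .30, and .42 is below the .77 that the SAP also cites.
- **That the .81 is the SAP's only assurance about treatment.** The section also gives .82 at d=.35 with 132 per group, and a calculation for time-averaged group differences after cutting 132 to 45 for clustering. The first makes no allowance for clustering. The second is labelled as covering the first two levels, whereas condition sits at level 3. They can be judged on their own terms and do not repair the .81.
- **That the trial is shown to be underpowered.** The powers in step 3 use a single outcome. The .81 concerns a time-averaged difference and Aim 1 tests a slope, so they do not transfer exactly to either parameter.

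The SAP already calls the examination of treatment effects with house characteristics exploratory, so that part of the remedy is partly in place.

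**Conclusion.** The target of the .81 is mis-described. With whole houses randomised, no house has a between-condition difference, and this part rests on the documents alone. As arithmetic, the figure fits only a one-predictor house-level main effect at f²=.25, where it is .81 approximately and .78 exactly.

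That main effect can be condition, but then the effect covered is about d=.42. For condition at .35 and .30, power is .63 and .50 with 32 houses, and it stays below .80 at .35 for each of the three house counts at ICC .06. With 32 houses it is also below .80 at ICC .01. These values depend on equal house sizes, 264 analysed, two-sided alpha .05 and a single outcome.

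The conclusion is therefore limited: no reading of the .81 supports the SAP's statement of ample power for the treatment comparison at .35 or .30. The planned analysis model is not affected.

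**What to change.** 1. Relabel the figure as power for the main effect of one house characteristic on a house-level outcome, and give .78 (exact) or say that .81 is a normal approximation.
2. Add power for the level 3 condition coefficient at .35 and .30, on the parameter actually tested. State whether that is the slope or a time-averaged mean.
3. Reconcile the house count (32, 70 or 30) first, and show a range of ICCs.
4. Revise the closing statement on adequacy of power to match.
5. If power for a condition-by-house-characteristic interaction is wanted, base it on the three-predictor model, state the noncentrality convention, and keep it labelled exploratory.

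The cost is SAP wording and one calculation. No data collection or design change is needed, but the stated power will be less favourable.

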A second exploratory aim is to conduct 30 qualitative interviews (15 in each condition) to identify general and intervention specific factors that were perceived to affect outcomes and ways to improve the two active interventions. An initial coding list will include specific codes suggested by characteristics of the intervention. For example, codes for the SLH alone condition might include things like “helped me increase support to not use alcohol or drugs,” and “helped me avoid exposure to alcohol and drugs.” For MMI, codes might include “made suggestions for services” and “helped me prepare for living at the SLH.” For meditation, codes might include things like “helped me relax” and “increased positive feelings about myself.” Using line-by-line coding, themes and excerpts of text will be highlighted as quotations that exemplify salient resident attitudes and beliefs. Excerpts will be printed out, and each analyst will group the excerpts into thematic categories. The extent of agreement between the analysts’ initial coding of the data will be assessed. Each analyst will define the working themes and through discussion select a final set. Data will be entered into the qualitative software program, N Vivo. The research team will use the constant comparison method and analytic memoing to identify patterns, create themes or categories, and develop theoretical insights (Strauss & Corbin, 1990).

Power Considerations

Given our sample of 165 in each of the 2 study conditions and our expectation that we will contact 80% of the sample at 12 months we should have 132 per group and a total N of 264 available for analysis for at least two time points. For tests of equality of paired differences in means for outcomes between the final interview and baseline between the two study conditions, power to detect small-to-medium effect sizes ($d=.35$) would be .82 in 2-sided tests with $\alpha=.05$.

Similar power is available for tests of equality of proportions (Cohen, 1988).

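### Power is called more than adequate, but the cited one-year effect (.30) is below the effect powered for (.35), and the stated .82 ignores randomization by house

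*SAP*

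**What the plan says.** All the power statements are in the SAP, under Power Considerations.

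- **Two-arm change test.** With 165 enrolled per arm and 80% retained at 12 months, 132 per arm are analysable. For the difference between arms in change from baseline to the final interview, "power to detect small-to-medium effect sizes ($d=.35$) would be .82", two-sided at alpha .05.
- **Longitudinal table.** For a time-averaged difference of .3 with three interviews, the table requires 65, 93 or 120 at within-person correlation .2, .5 or .8.
- **Design effect.** With an intraclass correlation of .06, the SAP reduces 132 to 45 effective respondents. It claims power close to .80 only at .35 and correlation .2.
- **House-level statement.** With 32 houses, power is .81 for f²=.25.
- **Conclusion.** A meta-analysis "found pairwise between group effect sizes to be .77 (very large) in the short term and .30 at (small-to-medium) one year follow up", and from this the section ends: "Therefore, power should be more than adequate".

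On the design, the protocol (Research Interviews) states: "Randomization will occur at the house level". The SAP (Analysis of Specific Aims, Aim 1) says that treatment "is implemented at the house level and therefore will be treated as a level 3 variable".

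**The concern.** The closing sentence draws reassurance from an effect smaller than the one the study was sized to detect. It also rests on a figure of .82 that treats residents as independent, although treatment is assigned by house and tested at house level. The between-arm hypotheses (H1.1 and H3.1 to H3.3) are all tested as differences in rate of change between arms. If readers believe these were amply powered at 12 months, they may take a null 12-month result as evidence that the intervention does not work, when the design had only a moderate chance of detecting the effect that the plan itself cites.

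**Working it through.** **Inputs from the documents.** 132 analysable per arm (264 in total), two-sided alpha .05, effects .35 and .30, intraclass correlation .06 and 32 houses (SAP, Power Considerations); 70 houses (protocol, Sample Characteristics and Design Summary).

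**Step 1: reproduce the plan's figure.** For a two-sample t test with n per arm, the noncentrality is d√(n/2). With n=132 and d=.35 it is .35 × 8.12 = 2.84, which gives power .81. This agrees with the stated .82 and leaves no room for a design effect.

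**Step 2: same test at .30.** The noncentrality is .30 × 8.12 = 2.44 and power is .68. For 80% power, 2 × 2.80²/.30² ≈ 175 per arm would be needed, against 132. No assumption about clustering enters this step.

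**Step 3: add the house design effect.** DE = 1 + (m − 1) × .06, where m is the number analysed per house, and effective n = 132/DE.

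| Basis | m | DE | Effective n per arm | Power at .35 | Power at .30 |
|---|---|---|---|---|---|
| No clustering | – | 1 | 132 | .81 | .68 |
| 70 houses | 264/70 = 3.77 | 1.166 | 113 | .75 | .61 |
| 32 houses | 264/32 = 8.25 | 1.435 | 92 | .66 | .53 |
| SAP's own adjustment | – | 1 + 32 × .06 = 2.92 | 45 | .38 | .29 |

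The last row is too severe: the SAP puts 32, its number of houses, where cluster size minus 1 belongs. It is shown because it is the plan's own figure.

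**Step 4: vary the intraclass correlation (assumed range).** At .02, power at .35 and .30 is .75 and .62 with 32 houses, or .79 and .66 with 70. Over .01 to .10, power at .30 runs from .65 down to .45 with 32 houses and from .67 down to .57 with 70.

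**Step 5: detectable effect at 80% power, intraclass correlation .06.** 2.80 × √(2/92) = .41 with 32 houses and 2.80 × √(2/113) = .37 with 70. With a t reference on house-level degrees of freedom (30 and 68) these become .43 and .38.

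**Step 6: the SAP's table.** At .3 it asks for 65, 93 or 120. The SAP has 45, so it falls short in every row by its own reckoning.

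**Step 7: the house-level statement.** For a balanced two-arm indicator, f²=.25 corresponds to a difference of 2√.25 = 1.0 SD of house means. With intraclass correlation .06 and 8.25 per house, that SD is √(.06 + .94/8.25) = .417 individual SD. The effect powered for is therefore about .42, again above .30.

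**The case against.** Six points can be made for the plan.

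- **The SAP does adjust for clustering.** It applies a design effect later in the same section and plans a three-level model. That is so; the criticism is confined to the .82 and to the closing sentence. The adjusted figures make that sentence harder to defend.
- **The .77 supports it.** For a short-term effect of that size, power is .95 even with 45 per arm. This stands, so the sentence fails for the one-year effect, not for both effects cited.
- **The corrected sample size rescues the table.** With 92 effective per arm, 65 is met, 93 is missed by one and 120 is not met; with 113, only 120 is missed. Time-averaged power at .30 with 92 is .91, .80 and .71 at correlation .2, .5 and .8. However, the table's entries match a one-sided alpha of .05; two-sided, these become .85, .70 and .59. More importantly, this target averages in the baseline interview, where the SAP expects no difference, while Aim 1 tests a difference in rate of change. With three equally spaced interviews, a linear slope contrast is the final-minus-baseline contrast, which is the test computed above.
- **Scale.** The .35 appears to be in SDs of change, and the scale of the cited .30 is not given. If .30 were in outcome SDs, it would equal .24, .30 or .47 change SDs at baseline-to-final correlation .2, .5 or .8. Power with 92 per arm would then be .36, .53 or .89. This is a real limit on precision and cuts both ways. The SAP sets the two figures side by side without converting them, and the check follows it.
- **The house-level comparison is approximate.** If outcomes are averaged over three interviews, the .42 becomes about .33 to .40. That is still above .30.
- **Only wording is affected.** True of the remedy, but the sentence claims a property that the design lacks at 12 months.

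**Conclusion.** The concern holds for the 12-month comparison. The stated .82 is correct arithmetic for independent residents at .35, but it is not the power of this house-randomized design, and the effect cited in support is smaller than .35. At .30, power is .68 without clustering, .61 with 70 houses and .53 with 32 houses at intraclass correlation .06, and .29 with the SAP's own effective sample. None of these reaches .80. The results assume that .30 and .35 are on the same scale, that the intraclass correlation of .06 applies to the change score, and that houses are of equal size. Describing power as close to even odds fits 32 houses; with 70 it is somewhat better but still short of 80%. The first conclusion, that .30 gives less power than was computed at .35, needs only the common scale.

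**What to change.** 1. Delete the closing claim of adequacy.
2. Reconcile the number of houses: 70 in the protocol's Sample Characteristics and Design Summary, 30 in its House Environment section, and 32 in the SAP.
3. Restate power for the 12-month between-arm comparison with a design effect based on residents analysed per house, at both .35 and .30. At intraclass correlation .06 this is .66 and .53 with 32 houses, or .75 and .61 with 70. State the scale of each effect size.
4. Add the effect detectable with 80% power: about .42 with 32 houses or .38 with 70.
5. If the .77 is kept, say that it bears on short-term effects only.

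The cost is SAP wording and a less favourable stated power. Enrolment, data collection and the analysis model are unaffected.
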